### 8.2 OBJECTIVE

The survey objective is to measure the effectiveness of the DHPC and EM, implemented as part of RMMs, by ascertaining the proportion of targeted physicians who understood and implemented the latest prescribing conditions and safety information about systemic thicolchicoside provided in the DHPC and EM.

Specific objectives were to evaluate the proportion of physicians who:

- prescribe systemic thicolchicoside only as adjuvant treatment of painful muscle contractures associated with acute spinal pathology in adults and in adolescents from 16 years onwards.
- do not prescribe systemic thicolchicoside for long-term treatment of chronic conditions.
- follow the recommendations regarding the doses and duration restriction:
  - for oral forms: the recommended and maximal dose is 8 mg every 12 hours, i.e. 16 mg per day. The treatment duration is limited to 7 consecutive days.
  - for IM forms: the recommended and maximal dose is 4 mg every 12 hours, i.e. 8 mg per day. The treatment duration is limited to 5 consecutive days.
- do not prescribe systemic thicolchicoside during pregnancy and lactation.
- do not prescribe systemic thicolchicoside in women of childbearing potential not using adequate contraception.

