### 5) Awareness of and attitude towards the latest prescribing conditions and safety information:

- Awareness of the prescribing conditions and safety information about systemic thiocolchicoside presented in the DHPC and EM:

- Awareness of the prescribing conditions and safety information: main concerns perceived
- Sources of knowledge
- Reception of the DHPC by the physician and awareness about the EM
- Physician's intention to consider the prescribing conditions and safety warnings

6) Recent prescriptions details:

The following information related to up to the last five prescriptions to patients will be collected upon physician's recall memory:

- Approximate date of prescription of systemic thiocolchicoside
- Approximate patient' age at the time of prescription (age ranges: <16 or ≥16 years old)
- Gender
- Status at the visit for females of childbearing potential (using or not an effective method of contraception, pregnant or not, planning to be pregnant, breastfeeding)
- Indication for which the drug was prescribed
- Form, number of administrations and dose per administration per day
- Duration of use prescribed
- Concomitant treatment(s) ongoing or written at the time of prescription
- Main reasons for choosing systemic thiocolchicoside
- Information and recommendations provided to the patient when prescribing systemic thiocolchicoside containing medicinal products.

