### **Sample of collected prescriptions:**

For the data on prescriptions, the statistical unit considered will be the individual drug prescription to patient. Although the level of contribution to this section per interviewed physician is not known and will depend both on the market sells of systemic thicolchicoside in each country and for each specialty, and on the percentage of interviewed physicians who prescribed the drug to patients. Physicians are requested to report up to 5 last prescriptions of systemic thicolchicoside written over the last 12 months before the survey, each pertaining to a unique patient.

As a result, the sampling method (systematic sampling) is expected to allow generalisability of results once the overall sample of physicians can be shown to be generalisable.

Based on IMS Medical Radar experience from previous similar surveys, it is estimated that in average each interviewed physician who prescribed systemic thicolchicoside to patients will contribute with 3 prescriptions on average.

If a conservative rate of 50% is assumed to evaluate the part of interviewed physicians who prescribed systemic thicolchicoside to patients, the sample size for prescriptions will be about 900, thus largely sufficient for the study of proportions of appropriate use of drug under the same assumptions of confidence interval and precision as described above.

Note that a sample adjustment will be also implemented for the sample of collected prescriptions using the same methodology as for analysable questionnaires but with different weights.

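### The prescription data record single courses only, with no first-or-renewal item, so they give an upper bound on adherence to the consecutive-day and long-term-use objectives

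*Protocol*

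**What the plan says.** Section 8.2 sets specific objectives as proportions of physicians. One is the proportion who "do not prescribe systemic thicolchicoside for long-term treatment of chronic conditions". Another is the proportion who follow the dose and duration restrictions. For oral forms, "The treatment duration is limited to 7 consecutive days"; for IM forms, "The treatment duration is limited to 5 consecutive days".

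Section 9.5.2 (sample of collected prescriptions) describes the behavioural data. Each physician reports at most five recent prescriptions, "written over the last 12 months before the survey, each pertaining to a unique patient". The unit of analysis is fixed in the same place: "the statistical unit considered will be the individual drug prescription to patient". The section expects about 900 prescriptions and considers that ample for estimating appropriate use.

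Section 9.3, item 6, lists what is recorded for each prescription: approximate date, age band, gender, childbearing status, indication, form and dose, "Duration of use prescribed", concomitant treatment, reasons for the choice, and information given to the patient. Item 3 of the same section asks for a 12-month total of prescriptions and specifies that patients are not being counted.

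**The concern.** Both objectives concern what one patient receives over time. The measurement is one prescription seen in isolation. If a physician writes a course of permitted length and then renews it without a break, the reported prescription still shows a permitted duration. The variable list has no item that would reveal the days before it.

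The error has one direction. Unseen renewals can raise apparent adherence but never lower it, so the apparent effectiveness of the DHPC and educational materials can only be overstated. This affects a central message: the English DHPC in Annex 4 says that the risk is highest when exposure is prolonged.

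**Working it through.** **Step 1. The protocol's own figures.** Physician sample: n = P(1−P)z²/e² = 0.25 × 1.96² / 0.04² ≈ 600, as stated in section 9.5.2. Prescriptions: 600 × 50% × 3 = 900, as stated. The half-width for 900 prescriptions treated as independent is 1.96 × √(0.25/900) = 3.3 points. No figure is in dispute. The point concerns what the 900 records can show.

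**Step 2. Objectives against variables.**

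| Departure from the section 8.2 objectives | Visible in the section 9.3 list? |
|---|---|
| One prescription longer than the stated limit for its form | Yes, from prescribed duration |
| Prescription for a chronic condition | Yes, if the indication is reported as chronic |
| Permitted-length course renewed without a break, same form | No |
| Permitted-length course directly after the other form | No |
| Repeated courses under an acute label | No |

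No other listed item fills the gap. The 12-month volume counts prescriptions rather than patients, so repeats per patient cannot be derived. The concomitant-treatment item might catch an overlapping second form, but not a completed earlier course.

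**Step 3. Is renewal a plausible route to longer use?** The labelling in Annex 5 caps packs at 30 × 4 mg and 14 × 8 mg (oral) and 10 × 4 mg (IM). At the daily maxima quoted in section 8.2 (16 mg oral, 8 mg IM), a full pack lasts:
- 30 × 4 / 16 = 7.5 days
- 14 × 8 / 16 = 7 days
- 10 × 4 / 8 = 5 days

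Longer treatment at that dose needs another pack, on the same prescription (visible) or on a later one (not visible).

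**Step 4. Illustrative size.** Let s be the share of prescriptions within the limit when read singly. Let r be the share of those that continue an earlier course and so take the total past the limit. Then true compliance = s(1−r) and overstatement = s × r. The documents give neither s nor r; both are assumptions.

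| s | r | True compliance | Overstatement (points) |
|---|---|---|---|
| 80% | 5% | 76% | 4 |
| 80% | 10% | 72% | 8 |
| 80% | 20% | 64% | 16 |

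In counts, 80% of 900 is 720 prescriptions; 5–20% of 720 is 36–144 read as compliant when they are not. Over s = 70–90% and r = 5–30%, the overstatement runs from 0.70 × 0.05 = 3.5 points to 0.90 × 0.30 = 27 points. At s = 80%, r = 5% already matches the planned 4-point half-width. Collecting more prescriptions narrows the interval but leaves this bias unchanged.

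**The case against.** **The questionnaire is not shown.** Annex 1 lists it as a stand-alone document, and the abstract introduces the prescription details with examples. It may contain a renewal item. This stands as a caveat: the finding rests on the section 9.3 list. If the item exists, section 9.3 should name it.

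**A reader might infer that the duration and long-term-use objectives cannot be answered from behaviour at all.** The documents do not support that. Prescribed duration exposes any single over-long course, and the indication can expose chronic use. The measure is incomplete but still informative.

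**A reader might also blame the one-prescription-per-patient rule.** That rule avoids duplication within patients. Dropping it would not help reliably, because the list contains no patient identifier with which to link two prescriptions. The gap is the missing history item.

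**The protocol has other evidence.** Knowledge and intention on duration are asked in the core questionnaire, but the section 8.2 objectives are worded as what physicians prescribe. The drug utilisation study may see repeat courses, and section 9.9.4 cites it as a reason for keeping this module simple. Section 7.3 places it in France and Italy, which hold 50.8% + 31.4% = 82.2% of prescriptions in Table 7.1–1. That is substantial cover, but its methods are not shown and it does not reach Greece or Portugal.

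**The limitation is already flagged.** Section 9.9.4 urges caution because of recall and selection bias. Neither is this problem: perfect recall would not supply a variable that is not collected.

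**No adherence score is defined.** Section 9.7.1 says only that the prescription variables are analysed by specialty. This stands: the overstatement arises when single-prescription durations are read against the limits, which is the only comparison the listed variables allow.

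**Conclusion.** The point holds as a measurement gap. On the listed variables, the prescription data give an upper bound on adherence to the consecutive-day and long-term-use objectives, and the error runs one way. Its size cannot be taken from the documents. The 4–16 points is an illustration that assumes 80% single-prescription compliance and 5–20% of those prescriptions continuing past the limit. A reader might equate the overstatement with the renewal rate itself (5–20 points), but that would require every prescription to look compliant when read singly.

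The gap affects what the survey may conclude on duration and long-term use. It does not affect the sample size, the sampling rule or the knowledge results. It is worth correcting before fieldwork because the change is small and the information cannot be recovered afterwards.

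**What to change.** Add one closed item to section 9.3, item 6, for each reported prescription: was this the first prescription for this episode or a renewal and, if a renewal, how many days of thiocolchicoside had already been prescribed without a break, recorded separately for oral and IM. Keep one prescription per patient.

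Report duration adherence in two ways: per single prescription, and on total consecutive days within the same form against the limit the protocol already states for that form. Describe oral/IM sequences without scoring them, because the documents define no combined limit.

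The cost is one more closed question within the roughly five minutes planned per prescription, plus one derived variable. The drawback is that it also relies on memory, in a module already open to recall bias.

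If the item is not added, state in section 9.9.4 and in the report that the duration results describe single prescriptions only. Limit the long-term-use and consecutive-day conclusions to match, and note that the drug utilisation study covers only France and Italy.

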#### 4.8 Study size

The sample survey will include physicians from the IMS OneKey reference lists.

The sample size calculation is based on the survey objective, *i.e.* to measure the effectiveness of the DHPC and EM, on the awareness and understanding of prescribers of systemic thicolchicoside about the latest prescribing conditions and safety information/warnings of systemic thicolchicoside provided in the DHPC and EM.

Since the expected proportion of physicians who received and understood the latest prescribing conditions and safety information of systemic thicolchicoside is not known and there is no evidence supporting it, the worst case hypothesis will assume a proportion of 50%. For a confidence interval of 95% and a precision of 4%, a total of 600 analysable web-questionnaires will be needed for the overall sample: 180 in France and Italy, and 120 in Greece and Portugal.

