**Table 9.5.2–1: Sample size obtained for various precisions and proportions**

Margin of error for 95% CI				
Proportion	5%	4%	3%	2%
10%	139	216	384	864

30%	323	504	896	2,017
50%	384	600	1,067	2,401
70%	323	504	896	2,017
90%	139	216	384	864

Since the proportion of physicians informed about the updated prescribing conditions and recommendations for safe use of systemic thiocolchicoside is not known and there is no evidence supporting the expected proportion, the worst case hypothesis will be assumed considering that 50% of physicians will have received and understood the safety information distributed recently. This assumption yields the largest sample size.

Considering this hypothesis and in order to achieve a CI of 95% with a half-width of 4%, a total of 600 analysable physician questionnaires will be needed for the overall sample. Considering a margin of error of 5% (or 3% respectively) instead of 4%, the required sample size would be 384 (or 1,067) analysable physician questionnaires for the overall sample.

Based on IMS Medical Radar experience from previous similar surveys and estimates and the evaluation of the survey feasibility with four countries, the sample size of 600 is considered for this study. Indeed, the elected sample size should be sufficient to be divided between 4 countries and further between 3 groups of specialities.

It is estimated that about 30% of physicians will not complete the questionnaire until the end or not be analysable (i.e. physicians who respond to questions regarding their knowledge on the updated safety concerns of systemic thiocolchicoside or physicians without any prescription of systemic thiocolchicoside in the last 12 months or physicians who have to interrupt the interview due to an emergency (rare)). Taking into account these respondent physicians without analysable questionnaires, the overall sample size of 780 participating physicians will be required to reach 600 analysable questionnaires (i.e. recruitment of physicians should continue until 600 analysable questionnaires have been reached).

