Free text answers to open-ended questions will be categorised by theme, listed according to the frequency.

Confidence intervals of 95% will be evaluated, when relevant.

The proportions of correct and appropriate answers to selected questions asked in the questionnaire will be expressed among physicians with complete analysable web questionnaires. The endpoint will be assessed overall, by country and among subgroups of physicians' specialty.

In a first step, calculations will be performed on raw data. No projection factor will be applied to generalize the results to the entire prescribers' universe. As a consequence, the line "Overall - unweighted results" will show only the results observed on the overall sample, and will not reflect the countries' universe since this sample is not proportional to the size of IMS OneKey reference files in each country.

In a second step, the results will be weighted according to the real proportion of physicians in each specialty and country in order to accurately reflect the population that the survey seeks to measure.

For each country, the results will be reported according to the prescribers' specialty distributed proportionally to their weight within IMS OneKey reference lists.

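### The physician-level prescribing objectives have no matching physician-level analysis or precision, and the 50% used to size the prescription block conflicts with the eligibility rule

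*Protocol*

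**What the plan says.** Section 8.2 opens its list with "Specific objectives were to evaluate the proportion of physicians who" and continues with prescribing behaviours: indication, no long-term use, dose and duration limits, and the pregnancy, lactation and contraception restrictions.

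The content of actual prescriptions is collected only in 9.3, item 6, from recall, for up to five recent prescriptions. Under the sample of collected prescriptions (end of 9.5.2), the statistical unit for these data is the single prescription, and 9.7.1 gives them a separate analysis by specialty. The physician-level study objective in 9.7.1 covers physicians who received, understood and agreed to implement the information. Correct and appropriate answers to selected questions "will be expressed among physicians with complete analysable web questionnaires".

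On size, 4.8 gives the basis as "For a confidence interval of 95% and a precision of 4" per cent, and 9.5.2 concludes that "a total of 600 analysable physician questionnaires will be needed for the overall sample". The proportion behind that figure concerns awareness: "the worst case hypothesis will be assumed considering that 50% of physicians will have received and understood the safety information distributed recently". For prescriptions, the plan says "If a conservative rate of 50% is assumed to evaluate the part of interviewed physicians who prescribed systemic thicolchicoside to patients" and that each such physician "will contribute with 3 prescriptions on average", so that "the sample size for prescriptions will be about 900".

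Three other provisions bear on this. Inclusion (9.2.1) requires prescribing in the previous 12 months, and 9.5.2 counts physicians without such a prescription as non-analysable. Missing values are excluded from percentages (9.6). Missing data are expected to be rare and random (9.7.1 and 9.7.3).

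**The concern.** There are two linked problems.

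First, the objective and the analysis use different units. Section 8.2 asks what share of physicians prescribe within the restrictions. The prescription analysis answers what share of prescriptions do so, and the physician-level analysis answers what share of physicians know the rules and accept them. Neither gives the quantity that 8.2 names, and no precision is stated for it.

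Second, the 50% has no consistent meaning. It is worded as the share of interviewed physicians who prescribed the drug, yet everyone in the analysable 600 must have prescribed it within the same 12-month window that the block covers. If it means instead the share who will fill in the block, up to half of the sample is blank on behaviour, which does not fit the missing-data premise.

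At stake is the implementation half of the research question. If contribution is incomplete, the behaviour results describe a self-selected part of the sample with lower precision, and the protocol does not tell the reader how large that part is expected to be.

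**Working it through.** **Inputs, all from the protocol.** 95% confidence, P = 50%, 600 analysable physicians (4.8, 9.5.2); 180 each in France and Italy and 120 each in Greece and Portugal (Table 9.5.2–3); 50% contributing, three prescriptions each, about 900 in total (sample of collected prescriptions).

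**Reproducing the plan's figures.**
- n = P(1−P)z²/e² = 0.25 × 1.96² / 0.04² = 600.
- Half-width = 1.96 × √(0.25/n): 4.0% at 600, 7.3% at 180 and 8.9% at 120, matching the stated 4%, 7% and about 9%.
- 600 × 0.50 × 3 = 900. A base of 780 participants would give 1,170, so the 50% is applied to the 600 analysable physicians. That implies 300 contributors.

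**The consistency check.** The 600 already exclude physicians with no prescription in the last 12 months, and the prescription block covers those same 12 months. The share of the 600 who prescribed is therefore 100% by definition, not 50%. The 50% can only describe willingness or ability to report.

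**Physician-level precision by share contributing.** Blanks are excluded as in 9.6; P = 50%, unweighted.

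| Share contributing | Physicians | Half-width |
|---|---|---|
| 100% | 600 | 4.0% |
| 80% | 480 | 4.5% |
| 70% | 420 | 4.8% |
| 50% | 300 | 5.7% |

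**By country, assuming the 50% share is equal everywhere.** France and Italy: 180 × 0.5 = 90, half-width 10.3%. Greece and Portugal: 120 × 0.5 = 60, half-width 12.7%.

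**Effect of weighting (approximate).** Variance = Σ (N_h/N)² × 0.25/n_h, with N_h from Table 9.5.2–2 (total 163,178) and n_h from Table 9.5.2–4. Rheumatologists outside France have no population count there and are left out. French GPs dominate: (90,630/163,178)² × 0.25/90 = 0.000857 of a total of about 0.001098. The half-width is 1.96 × √0.001098 = 6.5% if all 600 contribute. At 50% contribution in every stratum it is 6.5% × √2 = 9.2%.

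**What the 900 delivers.** 1.96 × √(0.25/900) = 3.3% if prescriptions are independent. This is precision for a proportion of prescriptions, so it does not fill the gap for a proportion of physicians.

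**The case against.** The strongest defence is that the protocol does define its physician-level endpoint: answers to the questionnaire, including intention to apply the conditions, scored among all complete questionnaires. That can be done for all 600. The prescriptions are a separate, per-prescription analysis in which a physician reporting none adds nothing to the denominator, and 9.9.4 already says that they will be interpreted with caution. This stands as a description of the plan. But agreement to implement is a different quantity from the prescribing that 8.2 lists, so the defence leaves the mismatch in place.

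Several stronger readings are tempting and are not supported:
- **That half of the physicians will supply nothing.** The 50% is labelled conservative and the contribution level is said to be unknown. It is a planning floor. The block is not described as optional; physicians are asked to report systematically.
- **That results could swing widely with how blanks are scored, as compliant or non-compliant.** Section 9.6 excludes missing values, so neither scoring is what the plan would do.
- **That the protocol promises 4% for physician-level prescribing.** It ties 4% to awareness and understanding and, separately, to the 900 prescriptions. Physician-level prescribing has no stated precision.

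It is also fair that 9.5.2 disclaims equal precision for subgroups, and that the details of a sensitivity analysis may sit in a statistical analysis plan that is not at hand. The unit of the objectives and the conflicting 50% are fixed in the protocol itself.

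**Conclusion.** The point holds in a limited form. The specific objectives are stated per physician, while actual prescribing is analysed only per prescription. The assumption that sizes the prescription block contradicts either the eligibility rule or the missing-data premise, depending on how it is read.

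If a per-physician prescribing result is produced under the plan's own exclusion rule, it rests on somewhere between about 300 and 600 physicians, with the half-widths tabulated above. The lower end assumes that the protocol's conservative 50% is realised. The country figures further assume that this share is the same in every country. The stated 600 and 4% remain sound, before weighting, for the awareness and understanding items.

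This does not invalidate the survey. It leaves the behaviour objectives without a matching estimate, denominator or precision, and all three can be supplied from data already to be collected.

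**What to change.** 1. In 9.5.2, reconcile the 50% with the 12-month prescribing requirement. If it means the share expected to report prescriptions, say so, and align the missing-data statements in 9.7.1 and 9.7.3.
2. In 9.7.1, state that each prescribing objective in 8.2 is also calculated per physician, among those reporting at least one prescription.
3. Report the number reporting none by country and specialty, and compare their knowledge answers with those of contributors. Add bounds, with non-contributors taken as all compliant and then all non-compliant, as a sensitivity analysis only.
4. State the precision for this denominator as a range: unweighted half-width at P = 50% of 4.0% with all 600, 4.5% at 80% and 5.7% at 50%. At 50% in every country, give about 10.3% for France and Italy and 12.7% for Greece and Portugal. Note that weighting widens all of these.
5. Keep the 600 and 4% statement for the awareness and understanding items.

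The cost is protocol wording, one extra table and a less favourable stated precision for the behaviour objectives. No additional physicians are needed.

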**Figure 1: Study scheme and main timelines**

#### 9.2.1 Inclusion criteria

The survey will be conducted among physicians meeting the following inclusion criteria:

- Physicians who prescribed systemic thiocolchicoside within the 12 months prior to the survey
- GPs and specialists of any of those targeted for the DHPC and EM:
  - Rheumatologists
  - Orthopedists / orthopedic surgeons

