## 9.5 STUDY SIZE

### 9.5.1 Sampling plan

The statistical unit considered is the physician who prescribes systemic thiocolchicoside. For each selected country, the sample survey will include physicians identified and recruited from one source: IMS OneKey reference lists of required specialists.

These lists may not cover all of the physicians who received the DHPC and EM or may include physicians who were not targeted for the DHPC and EM. Consequently a screening question will check whether the physician has prescribed systemic thiocolchicoside within the last 12 months and therefore can be considered as a prescriber. These lists will be restricted to the targeted specialists' population, i.e. selected specialists who are currently active and not retired in 2016 at the time of the survey.

As per sample size defined below and the number of selected countries and specialties, physicians will be stratified only per country and specialty (Table 9.5.1–1). Other criteria such

as region, age and gender of the prescriber are less relevant than country and specialty, since they may not be available in all countries or not be a determinant as important as country or specialty. The use of more strata would have needed a larger sample size.

A random stratified sampling method will be applied. As a first step, all lists will be merged, and then the eligible physicians will be divided into homogeneous groups, called strata, which are mutually exclusive (a physician can only belong to one stratum). This stratification will be based on the following criteria:

- Country: 4 possibilities,
- Specialty: 3 possibilities.

Thus,  $4 \times 3 = 12$  strata will be formed.

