#### Study objective:

The proportion of targeted physicians who received, understood and agreed to implement the latest prescribing conditions and safety information about systemic thiocolchicoside provided in the DHPC and EM will be evaluated. Analysis will be done in total and separately by specialty (GPs, rheumatologists and orthopaedists / orthopaedic surgeons) using proportions and the corresponding 95% Wald confidence intervals.

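### The precision claimed for about 900 prescriptions ignores clustering within physician and uses a 50% prescriber rate that eligibility rules out; separately, the objective on actual prescribing has no matching physician-level estimate

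*Protocol*

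**What the plan says.** For the main survey, section 9.5.1 sets the unit: "The statistical unit considered is the physician who prescribes systemic thiocolchicoside". Section 9.5.2 then uses the normal-approximation formula for a single proportion and arrives at 600 analysable questionnaires for a 95% interval with half-width 4% at an expected proportion of 50%.

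For the prescription data the unit changes: "the statistical unit considered will be the individual drug prescription to patient". On how they are gathered, the same paragraph says: "Physicians are requested to report up to 5 last prescriptions of systemic thicolchicoside written over the last 12 months before the survey". It expects that each prescribing physician "will contribute with 3 prescriptions on average", assumes that half of the interviewed physicians prescribed the drug, and concludes that "the sample size for prescriptions will be about 900, thus largely sufficient for the study of proportions of appropriate use of drug", under the same confidence and precision assumptions as the physician sample. It adds that prescriptions will be weighted by the same method as the questionnaires but with different weights, which it does not give.

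The inclusion criterion in section 9.2.1 reads "Physicians who prescribed systemic thiocolchicoside within the 12 months prior to the survey", and section 9.5.2 counts physicians without a prescription in the last 12 months among the non-analysable.

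Section 8.2 states the objective as the "proportion of targeted physicians who understood and implemented the latest prescribing conditions and safety information". Its specific objectives are all proportions of physicians who prescribe, or do not prescribe, in a given way. The study-objective analysis in section 9.7.1 instead concerns physicians who "received, understood and agreed to implement the latest prescribing conditions and safety information".

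**The concern.** Three things do not fit together.

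- **Clustering.** Prescriptions written by one physician share that physician's knowledge and habits, which are what the survey sets out to measure. Counting them as independent against a requirement of 600 independent units overstates the information they carry whenever the within-physician correlation is positive. The protocol gives no ICC or design effect, so its sufficiency claim has no support as written.
- **The 50% rate.** Non-prescribers are screened out over the same 12-month window that the prescription section covers. Among the 600 analysable physicians the share who prescribed is therefore 100% by definition.
- **The estimate for behaviour.** Actual prescribing is recorded only in the prescription section and analysed per prescription. The physician-level analysis reaches intention and stops there. No rule turns a physician's reported prescriptions into a statement about that physician.

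At stake are the reliability of the precision quoted for the prescribing results and whether the report can answer the behaviour objectives in the terms in which they are set.

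**Working it through.** **Inputs.** 600 analysable physicians, expected proportion 0.5 and half-width 0.04 (section 9.5.2); 50% contributing, mean of 3 and maximum of 5 prescriptions per physician (paragraph on the sample of collected prescriptions). The ICC is not in the protocol, so a range is assumed.

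**Reproducing the plan's figures.**
- Required n = 0.5 x 0.5 x 1.96² / 0.04² = 600.
- Prescriptions = 600 x 0.50 x 3 = 900.
- Half-width at 900 independent units = 1.96 x √(0.25/900) = 3.27%.

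**Allowing for clustering, before weighting.** Design effect = 1 + (m − 1) x ICC, and effective n = 900 / design effect. With exactly three prescriptions per physician, m = 3:

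| Assumed ICC | Design effect | Effective n | Half-width |
|---|---|---|---|
| 0 | 1.0 | 900 | 3.27% |
| 0.10 | 1.2 | 750 | 3.58% |
| 0.25 | 1.5 | 600 | 4.00% |
| 0.30 | 1.6 | 563 | 4.13% |
| 0.50 | 2.0 | 450 | 4.62% |
| 1.00 | 3.0 | 300 | 5.66% |

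The margin of 900 over 600 absorbs a design effect of 900/600 = 1.5, so the limit is ICC = 0.5/2 = 0.25.

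**Unequal counts averaging three.** Here m is replaced by Σm²/Σm.
- 1 to 5 equally likely: 55/15 = 3.67, so the limit is 0.5/2.67 = 0.19.
- Half report 1 and half report 5: 26/6 = 4.33, so the limit is 0.5/3.33 = 0.15.

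**Count consistent with eligibility.** 600 x 100% x 3 = 1,800, if the mean of three still applies.
- With three each, effective n = 1,800/(1 + 2 x ICC): 1,500 at ICC 0.1, 900 at 0.5 and 600 at 1. The half-widths are 2.53%, 3.27% and 4.00%, so the target holds at any ICC.
- With unequal counts, the tolerable design effect is 1,800/600 = 3. The limits become 2/2.67 = 0.75 and 2/3.33 = 0.60.

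**Objective against estimate, for actual prescribing.**

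| | Unit | Quantity |
|---|---|---|
| Section 8.2 | physician | implemented the conditions |
| Section 9.7.1, study objective | physician | agreed to implement them |
| Prescription sample (9.5.2) and prescription analysis (9.7.1) | prescription | what was prescribed |

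No row of the analysis matches the first row.

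**Per-prescription and per-physician rates differ.** Suppose, as an illustration only, that 90% of prescriptions comply, independently. The share of physicians with all three compliant is then 0.9³ = 73%.

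**The case against.** Much can be said for the plan.

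- **The 4% may well be met.** It would be tempting to say the prescription sample is too small. The documents do not support that. Unweighted, 900 absorbs a design effect of 1.5, and the eligibility-consistent 1,800 absorbs far more. The 50% error understates the sample, and the protocol itself calls the rate conservative. What stands is that sufficiency is asserted without the quantity on which it depends.
- **The size of the weighting loss is unknown.** A reader might combine clustering with weights by prescription volume and obtain ±5.4% to ±7.0% for ICC 0.1 to 0.5. Most of that widening comes from the weights: on such weights 900 falls to about 388 even at ICC 0. The protocol does not specify those weights. Table 7.2–1 has no specialty data for Greece or Portugal, and section 7.4 warns that the panel omits some specialties in France and Italy. Only the direction of the loss can be asserted.
- **No variance method is stated for prescriptions.** The Wald interval in section 9.7.1 belongs to the physician-level objective. A clustered variance may be in an analysis plan that is not shown, so it cannot be said that the prescription intervals will be too narrow. The sufficiency sentence, however, is in the protocol.
- **Most of the objective is on the right unit.** Knowledge, awareness and intention are analysed per physician (sections 9.7.1 and 9.7.3). To say that the objective as a whole is answered on the wrong unit would go too far; the mismatch is confined to actual prescribing.
- **The prescription section is already caveated.** Section 9.9.4 calls it prone to recall and selection bias and separates it from the core questionnaire. Section 7.2 places the survey alongside a drug utilisation study. This lowers the stakes but does not reconcile sections 8.2 and 9.7.1.

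**Conclusion.** The point holds in limited form and should be fixed. The sufficiency claim compares clustered prescriptions with a requirement for independent units, and its 50% rate contradicts the protocol's own eligibility rule.

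For an assumed ICC of 0.1 to 0.5 and three prescriptions each, 900 prescriptions carry the information of 750 to 450 before weighting. The 4% target is lost above ICC 0.25, or above about 0.15 to 0.19 with unequal counts. The 1,800 implied by eligibility meets it at any ICC with three each. These results rest on an ICC that the protocol does not give, on the mean of three and, for 1,800, on every eligible physician reporting. Unequal prescription weights would reduce precision further in either case, by an amount that cannot be fixed from the text.

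Separately, the physician-level objective on implementation has no planned estimate: the analysis delivers intention per physician and behaviour per prescription. The core knowledge and intention estimates are unaffected.

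**What to change.** - **Restate the sample.** Replace the sentence on 50% and 900 with a count consistent with the inclusion criterion, or say that 50% means willingness to report prescriptions. Give the resulting precision over a stated ICC range and after the planned weighting, and drop the claim of ample sufficiency.
- **Cluster by physician.** Compute confidence intervals for prescription-level proportions with the physician as the cluster.
- **Align objective and estimate.** Report agreement to implement as intention. Then either reword the behaviour objectives as proportions of prescriptions, or add a physician-level compliance measure.

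A physician-level measure must account for the number of prescriptions reported. A rule that every reported prescription must comply would favour those who report few: at 90% independent compliance, a physician reporting one passes 90% of the time and one reporting five passes 0.9⁵ = 59%. If only 300 physicians contribute, the half-width of such a proportion is 1.96 x √(0.25/300) = 5.66% before weighting. It should carry the recall caveat of section 9.9.4.

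The cost is protocol wording and analysis programming. The variables are already planned in section 9.3, so no new data items are needed.
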